6.3 Study Duration

The study duration is 3 years. Subjects will only be followed for as long as the individual investigator or individual subject agrees.

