	
crisis".
 
 4. Despite being on or having standard of care and still has pain (>3 on the Pain NRS); and 5. Signed and dated written informed consent from the subject. 
Exclusion criteria
 
 1. Pregnant or lactating females or females who are planning a pregnancy during the study; 2. Positive pregnancy test at screening; 3. Major organ failure, renal, lung and liver failure; 4. Participants having active liver disease or unexplained persistent elevation of serum transaminases > 3 times the upper limit of normal; 5. Participants with a creatinine clearance < 60mL/min; 6. History of cardiac or respiratory failure; 7. History of recent myocardial infarction or poorly controlled ischaemic heart disease; 8. Severe respiratory disease (e.g., GOLD 3 for COPD or asthmatics requiring high doses of oral corticosteroids). 9. History or presence of alcohol or substance abuse, including analgesics used as standard of care. 10. Participation in a clinical trial of an investigational medicinal product; 11. With any known or suspected history or family history of schizophrenia, or other psychotic illness; history of severe personality disorder or other significant psychiatric disorder disorders other than depression associated with their underlying condition. 12. Known hypersensitivity to cannabis or allergy to cannabis or CBMP and 13. Direct employee of the study site.

Test product, dosage and mode of administration
	
The treatment regimen is as follows. In addition to standard of care management provided by their regular health care practitioner, participants will receive defined doses of inhaled CBMP namely Equipose 8-8 with a balanced ratio of THC and CBD as a dried cannabis flower.
 
Inhaled delivery
 
Cannabis flower containing mid and balanced levels of THC and CBD (Equipose 8-8), will be vaporised using a CE marked, handheld device with dose counting and Bluetooth connectivity to a smart device (Ryah).
 
Dosing will be recorded by the study participant entering their data into the ePRO data collection system through an application on their mobile phone. Participants will receive prompts to enter data and must do so to continue in the study.

Duration of treatment
	
3 years

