6.4.4 Study Drug Discontinuation

Reasons for the discontinuation of study drug may include, but are not limited, to the following:

1. An AE, SAE, drug reaction, or complication, whether related or not to the treatment drug, which precludes continuation of dosing with study drug.
2. Abnormal laboratory results that lead the Investigator to diagnose a poorer prognosis for subject health.
3. Noncompliance with study drug dosing.
4. Noncompliance with study procedures.
5. Subject's right to withdraw consent at any time during the study, with or without a stated reason.
6. Three separate pieces of evidence that the subject is self-administering other cannabis treatments outside of the prescribed study treatment (three strikes rule). Prior users of non-prescription cannabis will be monitored for any indication that they are using non-trial sources of CBMP, through regular explicit questioning and monitoring of patient reported outcome responses.
7. The investigator's opinion that it is not in the subject's best interest to continue study participation.
8. Sponsor's decision to terminate the study.
9. Pregnancy.

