6.4.5 Premature removal from study

Participants may withdraw from the study at any time at their own request, or at the discretion of the investigator or sponsor for safety, behavioural, or administrative reasons. If a participant does not return for a scheduled visit, every effort will be made to contact them and to document participant outcome, wherever possible. The investigator will establish the reason for withdrawal. If the participant withdraws consent for disclosure of future information, no additional data will be collected for the study. The sponsor will retain and continue to use any data collected before such withdrawal of consent.

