6.4.8 Study Treatment Discontinuation

The primary reason for study treatment discontinuation will be documented as extensively as possible. Subjects who discontinue study treatment prematurely will be followed-up until the end of study, or until they withdraw consent.

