6.5.1 Treatments administered

The treatment regimen will be as follows; a vaporised/inhaled medical cannabis strain (CBMP), namely Equipose 8-8 with a balanced 8% THC and 8% CBD content. Treatment is a full spectrum medical cannabis product presented as dried flower:

The cannabis will be delivered by a smart vaporiser device manufactured by Ryah. This is CE marked having passed CE-RED NB and IEC 60601 medical device safety tests. It is a temperature-controlled vaporiser with flow sensors that connects remotely with a smart-device. hosted application which collects dosing data from the vaporiser and patient reported outcomes, permitting further dosing only after completion of required data entry. The CBMP is placed in a prefilled cartridge which contains 250 mg of product. This cartridge is QR coded and must be read by the mobile application prior to loading into the vaporiser. Detailed instructions on how to use the vaporiser will be provided with each vaporiser and a UK-based technical helpline will be provided in case the subject needs to be assisted with vaporiser use.

Treatment is determined by the study Physicians based on the subject's medical history, their subtype of chronic pain and their experience with CBMP use. Study Physician will be given extensive guidance on state of the art of CBMP prescribing, ensuring that subjects can tolerate the CBMP and are not given a dose of THC that might cause excessive adverse events. All subjects will be prescribed an initial low dose of CBMP. Real-time evaluation of efficacy and tolerability will allow dose to be titrated appropriately.

Using the principles of universal precaution all subjects will start the protocol at a low dose. At the low dose the subject will commence with one 1 vape session (250 mg of cannabis) in the evening only. All subjects will progress to the higher dose at 1 month after baseline, unless

instructed not to by the study clinician, who will review how well the subject has tolerated the CBMP. The higher dose will consist of 2 vape sessions (250 mg total cannabis flos per cartridge) one in the morning and one in the evening.

6.5.2 Selection of doses in the study:

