9.2 Determination of Sample Size

The sample size was calculated based on the objective of showing a greater proportion of patients experiencing an improvement in NRS score, from baseline to 12 months, when using CBMP in addition to the standard of care as compared to the standard of care alone. We assume that 25% of matched controls will experience an improvement in NRS score (O'Brien and Breivik, 2011). A sample size of 3600 patients using CBMP plus 3600 matched controls will provide at least 80% power to detect an increase in the proportion of patients experiencing a 28% improvement, using a two-sided z-test test for proportions with a Type I error rate of 5%. After adjusting for 10% non-evaluable rate and a 20% match failure rate, the sample size is 5000 CBMP patients plus 5000 matched controls.

Thus the null hypothesis $H_0: P=0.8$ is tested against the one-sided alternative $H_1: P>0.80$. Assuming that the expected pain reduction at 18 months for the treated subjects is $P_1=86\%$, a minimum sample size of 500 subjects for each type of chronic pain, with a total minimum number of 5000 subjects, is needed to design the study at 80% power, using a one-sided level 0.05 test for single proportion and the variance from the empirical estimate.

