9.3 Analysis Sets

Data from all subjects recruited to the study will be analysed using an Intention-to-treat (ITT) approach, therefore data will be included in the primary analysis irrespective of whether the stipulated dose regimen or all the study medicines were followed throughout the study. All participants who receive at least one dose of any of the study drugs will be included in the safety analysis set (SAF). A Per Protocol (PP) analysis may also be conducted, comprising those subjects who adhere to the regimen as per protocol, as defined by the database entry and excluding subjects with major protocol deviations.

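### Draft CANPAIN protocol: section 6.3 and the synopsis let outcome follow-up end on grounds that conflict with 6.4.8 and with the ITT commitment in 9.3

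*Protocol*

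**What the plan says.** All the passages are in the draft CANPAIN protocol appended to the feasibility protocol.

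- **Section 6.3 (Study Duration):** "Subjects will only be followed for as long as the individual investigator or individual subject agrees". The investigator's agreement is not tied to any reason.
- **Synopsis (test product, dosage and mode of administration):** "Participants will receive prompts to enter data and must do so to continue in the study".
- **Section 6.4.8 (Study Treatment Discontinuation):** "Subjects who discontinue study treatment prematurely will be followed-up until the end of study, or until they withdraw consent".
- **Section 9.3 (Analysis Sets):** "Data from all subjects recruited to the study will be analysed using an Intention-to-treat (ITT) approach". It adds that data count in the primary analysis whether or not the regimen was followed.
- **Section 6.4.5 (Premature removal from study):** a participant may leave on request, "or at the discretion of the investigator or sponsor for safety, behavioural, or administrative reasons". The same section asks for every effort to contact those who miss a visit and to document their outcome.
- **Section 7.4 (Actions to be undertaken):** after an adverse event or concurrent condition, the study doctor decides whether to withdraw the subject from the study.
- **Section 6.4.4 (Study Drug Discontinuation):** the reasons for stopping study drug include "Noncompliance with study procedures".
- **Section 6.5.1 (Treatments administered):** the device application is described as "permitting further dosing only after completion of required data entry".

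**The concern.** An ITT analysis needs outcomes from patients who stop treatment. Section 6.4.8 provides for this with two end points only: end of study, or withdrawal of consent. Section 6.3 adds a third, the investigator's agreement, and the synopsis a fourth, failure to enter data. A site reading these passages cannot tell whether a patient who stops using the app is off drug or out of the study.

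The study is non-randomised and unblinded, with controls drawn from other sites. The investigator who may end follow-up therefore knows that the patient is treated and how the patient is doing. It is plausible, though the protocol gives no data on it, that patients with little benefit or poor tolerability stop dosing and data entry more often. If their outcomes are then lost, and lost more often than those of comparable controls, the treated cohort looks better than it is.

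**Working it through.** **1. The passages side by side**

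| Passage | What can end outcome follow-up |
|---|---|
| 6.4.8 | End of study; withdrawal of consent |
| 6.3 | Investigator or subject no longer agrees, no criteria |
| Synopsis | Failure to enter data |
| 6.4.5 | Own request; investigator or sponsor discretion, for three classes of reason |
| 7.4 | Study doctor's decision after an adverse event or concurrent condition |
| 6.4.4, 6.5.1 | Nothing: non-compliance or missing entries affect the drug only |

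The subject's own right to leave is already covered by 6.4.5 and 6.4.8. What 6.3 adds is investigator discretion that is wider than in 6.4.5. Read literally, 6.3 and the synopsis contradict 6.4.8. The passages in 6.4.5 and 7.4 also let the investigator end participation without saying whether outcomes are still collected.

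**2. The plan's own sample size (section 9.2)**

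Inputs: "We assume that 25% of matched controls will experience an improvement in NRS score"; 3600 per group; at least 80% power; two-sided 5%; 10% non-evaluable; 20% match failure; 5000 per group. The wording around 28% is unclear. It is read here as a 28% response in treated patients, because other readings do not fit 3600: 25% versus 53% needs 47 per group, and 25% versus 32% (a 28% relative increase) needs 652.

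- Power for 25% versus 28% with 3600 per group is 82.2%, which meets the stated level.
- 3600 / (0.90 × 0.80) = 5000, as stated.

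On this reading the target difference is 3 points.

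**3. How selective loss moves the treated rate**

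Assumptions, none of them given in the protocol: the true response is 25% in both groups, treated patients alone are lost, and only observed cases are analysed. Let L be the fraction of treated patients lost and m the share of those lost who are non-responders. Then

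observed treated rate = [0.25 − L(1 − m)] / (1 − L).

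With L = 0.10:

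| m | Calculation | Observed rate | Shift (points) | 3600 v 3600 test favours treatment |
|---|---|---|---|---|
| 100% | 0.25 / 0.90 | 27.8% | +2.8 | about 76% of null trials |
| 90% | 0.24 / 0.90 | 26.7% | +1.7 | about 36.5% |
| 80% | 0.23 / 0.90 | 25.6% | +0.6 | about 8% |
| 75% (non-selective) | 0.225 / 0.90 | 25.0% | 0 | no bias |

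To reach 28% with no true effect when only non-responders leave, L = 1 − 0.25/0.28 = 10.7%.

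**4. When controls are lost too**

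- Same L and m in both groups: both observed rates move equally, so the spurious difference is 0.
- 10% lost in treated and 5% in controls, m = 90% in each: treated 0.24 / 0.90 = 26.7%; controls (0.25 − 0.005) / 0.95 = 25.8%; difference about 0.9 points.

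**The case against.** **The synopsis sentence may only describe the dosing lock.** Section 6.5.1 ties missing entries to further dosing, 6.4.4 makes non-compliance a reason to stop the drug, and quarterly visits or calls do not depend on the app. This is a fair reading of intent, and no passage says that visits cease. But the synopsis speaks of continuing in the study, so the wording still has to be reconciled.

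**The loss need not fall on one arm.** A reader might infer that these rules act on the treated cohort only. The protocol does not support that. Section 6.2 says control data will mirror the CANPAIN data apart from tolerability, 6.3 refers to subjects in general, and nothing promises complete follow-up of controls. The app and dosing condition does concern treated patients. The follow-up rule for controls is simply not stated.

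**The 10% is not a treated-arm dropout rate.** Section 9.2 applies the non-evaluable and match-failure allowances to both groups. The 10% used above is a convenient size for an illustration and no more.

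**Missing data are left to the SAP.** Section 9.5.1.1 says so, and that is not a fault. But a SAP cannot restore outcomes that the protocol lets sites leave uncollected.

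**This is a draft with exploratory analyses.** That is true: the REC did not accept the CANPAIN protocol, p-values are to be read descriptively (9.1), and the objectives of the 3-month feasibility study are untouched. However, section 2 of the feasibility protocol says that the work is to support resubmission of CANPAIN, so the text can still be corrected.

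**Conclusion.** The contradiction stands on the text alone. Section 6.3 and the synopsis, followed literally, end follow-up in cases where 6.4.8 requires it and 9.3 needs it. Sections 6.4.5 and 7.4 leave the same question open.

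The bias is conditional. It requires loss that is related to response and greater in the treated cohort, and an analysis that does not correct for it. The protocol gives no dropout rate by response, so the range in the table, from none to 2.8 points for a 10% loss, is as far as the documents go. A reader might infer that dropout could manufacture the whole 3-point target. That is a worst case: it needs about 10.7% of treated patients to be lost, all of them non-responders, with no loss in controls. It is not a forecast. Because the target difference is small, even moderate selective loss would matter, and that is reason enough to settle the wording.

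**What to change.** 1. In 6.3, delete the reference to the individual investigator, so that follow-up no longer depends on that person's agreement.
2. Reconcile the synopsis, 6.3, 6.4.5, 6.4.8 and 7.4. They should say consistently that stopping treatment, missing app entries, or withdrawal by the investigator does not by itself end outcome collection.
3. State that pain NRS and SF-12 continue to be collected at the 3-monthly visit or call until consent is withdrawn. Table 1-1 already marks the pain NRS and quality-of-life rows at these contacts and allows them by phone. Section 6.6.1 lists pain NRS only as a weekly item, so it should be aligned.
4. State the same follow-up rule for the matched controls.

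This concerns outcome follow-up only. Rules on access to treatment are for the sponsor to reconcile.

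The cost is wording, plus some continued quarterly contacts with subjects who are off treatment.

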6.4 Selection of Study Population

6.4.1 Inclusion Criteria

Participants must meet all the following inclusion criteria to be eligible for enrolment into the study;

DRAFT

1. Male or female 18-85 years old;
2. Diagnosed with chronic non-cancer pain
3. A consented patient at the Harley Street (CPC) clinic.
4. Is receiving standard of care therapy with inadequate response or has completed standard of care treatment, does not want standard of care treatment, or standard of care is contraindicated (Inadequate response is defined as the subject receiving standard analgesic agents and still has pain, has unpleasant side effects or wishes to reduce their intake of standard of care analgesic agents, e.g. a subject receiving opioids who wishes to dose reduce in light of the "opioid crisis");
5. Despite being on or having standard of care and still has pain (>3 on the Pain NRS); and
6. Signed and dated written informed consent from the subject.

6.4.2 Exclusion criteria

Study exclusions will be assessed by the study clinician in light of established cannabis restrictions. However, in general participants meeting any of the following exclusion criteria will not be included in the study;

1. Pregnant or lactating females or females who are planning a pregnancy during the study;
2. Positive pregnancy test at screening;
3. Major organ failure, renal, lung and liver failure;
4. Participants having active liver disease or unexplained persistent elevation of serum transaminases > 3 times the upper limit of normal;
5. Participants with a creatinine clearance < 60mL/min; History of cardiac or respiratory failure;
6. History of cardiac or respiratory failure;
7. History of recent myocardial infarction or poorly controlled ischaemic heart disease;
8. Severe respiratory disease (e.g., GOLD 3 for COPD or asthmatics requiring high doses of oral corticosteroids).
9. History or presence of alcohol or substance abuse, including analgesics used as standard of care.
10. Participation in a clinical trial of an investigational medicinal product;
11. With any known or suspected history or family history of schizophrenia, or other psychotic illness; history of severe personality disorder or other significant psychiatric disorder other than depression associated with their underlying condition.
12. Known hypersensitivity to cannabis or allergy to cannabis or CBMP and
13. Direct employee of the study site.

6.4.3 Contraceptive Guidance

The safety and tolerability of medicinal cannabis has been studied and the adverse event and safety profile is well understood. The use of CBMP is not advisable during pregnancy, therefore we will ask for provision of evidence of a negative pregnancy test for women of child-bearing age, before treatment can commence. Evidence of a negative pregnancy test for women of child-bearing age (section 3.1 for definition) needs to be provided at screening and 3 months after the completion of the treatment period. It is mandated that males and females of a child bearing age use an acceptable barrier methods of contraception (see section 3.1 for definition) is used during the duration of the study (irrespective of whether the participant is using a hormonal contraceptive) from screening throughout the study and for 3 months after the last dose of the study treatment. The effectiveness of systemically acting hormonal contraceptives may be reduced by CBMP, therefore female participants using systemically acting hormonal contraceptives must add an additional second barrier method.

6.4.4 Study Drug Discontinuation

Reasons for the discontinuation of study drug may include, but are not limited, to the following:

1. An AE, SAE, drug reaction, or complication, whether related or not to the treatment drug, which precludes continuation of dosing with study drug.
2. Abnormal laboratory results that lead the Investigator to diagnose a poorer prognosis for subject health.
3. Noncompliance with study drug dosing.
4. Noncompliance with study procedures.
5. Subject's right to withdraw consent at any time during the study, with or without a stated reason.
6. Three separate pieces of evidence that the subject is self-administering other cannabis treatments outside of the prescribed study treatment (three strikes rule). Prior users of non-prescription cannabis will be monitored for any indication that they are using non-trial sources of CBMP, through regular explicit questioning and monitoring of patient reported outcome responses.
7. The investigator's opinion that it is not in the subject's best interest to continue study participation.
8. Sponsor's decision to terminate the study.
9. Pregnancy.

6.4.5 Premature removal from study

Participants may withdraw from the study at any time at their own request, or at the discretion of the investigator or sponsor for safety, behavioural, or administrative reasons. If a participant does not return for a scheduled visit, every effort will be made to contact them and to document participant outcome, wherever possible. The investigator will establish the reason for withdrawal. If the participant withdraws consent for disclosure of future information, no additional data will be collected for the study. The sponsor will retain and continue to use any data collected before such withdrawal of consent.

6.4.6 Withdrawal due to an adverse event

Withdrawal due to an adverse event should be distinguished from that due to participant perceived lack of treatment response or any other reason for withdrawal and this will be recorded. The study doctor must report this event to the study sponsor. The sponsor clinician must determine if this adverse event was as a result of the study medication. If this is the case the sponsor clinician must report the case to the regulator on an appropriate adverse event form. If this has implications to other participants, all study doctors must be immediately informed and subjects that are at risk must be immediately contacted and all or part of their treatment as appropriate must be stopped. Any future subject that may be impacted by this adverse event must not be recruited into the study or treated at the clinic.

If a participant withdraws due to a serious adverse event, the serious adverse event must be reported in accordance with the reporting requirements defined in Section 7.3 and if this has application to other subjects, all study doctors must be immediately informed and subjects that are at risk must be immediately contacted and all or part of their treatment as appropriate must be stopped. Any future subject that may be impacted by this adverse event must not be recruited into the study or treated at the clinic.

If a serious adverse event is determined to be at least possibly related to one of the treatment drugs and a change to the study management is warranted, the trial will be stopped as per current legislation and UK guidance. Any resultant change to the protocol which is to be implemented will be notified to the REC and MHRA via a substantial amendment. If a change is required

immediately to protect the safety of trial participants, then notification of Urgent Safety Measures will be made to the REC and MHRA according to the current legislation and UK guidance.

